Postoperative pain control is an area of active investigation as inadequate pain management can lead to an increased length of stay, readmission, chronic pain, and opioid dependence.¹⁻³ For laparoscopic hysterectomy, several non-opioid alternatives to pain management have been evaluated in an attempt to reduce patients' pain and minimize opioid consumption. These include local anesthetics, transversus abdominis plane blocks, anticonvulsants, non-steroidal anti-inflammatory medications, and steroids. Non-opioid pain management techniques have demonstrated varying success, with a few methods providing short-term improvements in patients' pain as well as opioid-sparing benefits.⁴ Superior hypogastric plexus block (SHPB) or presacral nerve block is another method that has shown promising results in patients undergoing abdominal hysterectomy; however, has not been evaluated in patients undergoing laparoscopic hysterectomy.

The superior hypogastric plexus lies in the presacral space and supplies autonomic innervation to the pelvis. This plexus has been implicated in chronic pelvic pain with studies demonstrating reduced pain scores and opioid use following image-guided percutaneous blockade or surgical transection of the plexus.⁵⁻⁹ To our knowledge, only one study has investigated the efficacy of a SHPB at the time of hysterectomy.¹⁰ This study was a double-blind randomized controlled trial of 68 women undergoing an abdominal hysterectomy, randomized to a presacral injection of 20 mL of ropivacaine versus saline. Sixty-three percent of women in the ropivacaine group had a VAS pain score less than 4 at two hours postoperatively, compared to 25% in the placebo group ($p=0.015$). Median opioid consumption was also less at 55.8 mg for the treatment group versus 72.4 mg for the placebo group ($p=0.032$). There were no side effects or adverse events reported in this study. We hypothesize that a SHPB will provide similar benefits in patients undergoing a laparoscopic hysterectomy.

VII. Objectives:

The objective of this study is to assess the efficacy of a SHPB for pain relief following laparoscopic hysterectomy. The superior hypogastric plexus lies in the presacral space and supplies autonomic innervation to the central pelvis. This plexus is suspected to play a role in postoperative pain following a hysterectomy. We hypothesize that a SHPB using the anesthetic bupivacaine will reduce patients' pain scores and opioid consumption following a laparoscopic hysterectomy.

VIII. Trial design:

This study is designed as a multi-center, randomized, single-blind, controlled trial of patients scheduled for a laparoscopic hysterectomy. Patients will be randomized to two groups: one group will receive a SHPB and laparoscopic hysterectomy, and the other will receive no block and laparoscopic hysterectomy.

METHODS

IX. Study setting:

The study will be conducted at three sites: Brigham and Women's Hospital (BWH)/Brigham and Women's Faulkner Hospital(FH), University of North Carolina Medical Center (UNC) and George Washington University (GWU).

X. Eligibility criteria:

Patients over 18 years of age who are scheduled for a laparoscopic hysterectomy at participating sites will be recruited to participate. Patients of all comorbidities will be eligible for inclusion; specifically, patients with chronic pain syndromes will not be excluded so as to evaluate the efficacy of SHPB in this population. The exclusion criteria include patients who are unwilling to consent, who have an allergy to block medications used in the trial, are undergoing a sacrocervicopexy or a sacrocolpopexy, are undergoing a laparotomy, or those with anatomy that limits the safe application of a presacral injection (per the surgeon's discretion at the time of the procedure). Patients will not be excluded if they undergo other concomitant procedures during laparoscopic hysterectomy. While concomitant procedures may contribute to patients' pain following laparoscopic hysterectomy, this will improve the external validity of the trial. Moreover, randomization should balance differences in patients and procedures between the two treatment arms.

XI. Interventions:

If the patient is randomized to a SHPB, it will be performed laparoscopically by the gynecologic surgeon at the start of the hysterectomy procedure. The SHPB block will contain 10 mL of 0.25% bupivacaine hydrochloride (2.5 mg/mL = 25 mg). The injection will be performed by tenting the presacral peritoneum, aspirating with a laparoscopic needle-tip syringe to ensure extravascular placement, and injecting the block with the laparoscopic needle-tip syringe (Appendix XXXIV). Patients in the control arm will undergo the planned procedure with no intervention. Following the procedure and intervention, surgeons will be

asked to complete a worksheet to assess the feasibility and safety of presacral injection, as well as details regarding the procedure (Appendix “SHPB MD Worksheet”).

All participants will undergo a surgically-indicated laparoscopic hysterectomy as planned. As per routine practice, all patients will also receive an incisional anesthetic using 20 mL of 0.25% bupivacaine at the laparoscopic port sites. Patients in the intervention group will additionally undergo a SHPB (10 mL of 0.25% bupivacaine laparoscopically injected in the presacral space) at the start of the procedure. The surgical risks of a SHPB are similar to any surgical procedure and include bleeding, infection, and injury to surrounding vessels and organs. These risks are expected to be very rare as all participating surgeons are expert laparoscopists who have safely operated in the presacral space. Viewing a video demonstrating this technique will also be required of all participating surgeons prior to the study. If a patient’s anatomy or pathology prohibits the safe application of a SHPB then the intervention will be abandoned.

All surgeons who will enroll patients from BWH, FH, UNC and GWU are experienced laparoscopic surgeons who have performed at least 100 advanced laparoscopic procedures including hysterectomy. Laparoscopic hysterectomy will be performed by the participating surgeons in the usual fashion, with inherent operator-dependent variation in technique. All participating surgeons will be required to view a video describing the technique of SHPB to ensure the procedure is performed similarly in all patients.

In an effort to reduce external factors that may influence postoperative pain, patients will be standardized to similar preoperative and postoperative medications. The standard preoperative medication regimen will include Celecoxib 200 mg po, Tylenol 975 mg po and Gabapentin 900 mg po. Patients will also receive the standard incisional anesthetic with 20 mL of 0.25% bupivacaine hydrochloride (2.5 mg/mL = 50 mg, combined with block totals 75 mg, max dose 2mg/kg therefore safe in all patients with weight over 37.5 kg). Patients will receive intraoperative narcotics at the discretion of the anesthesia team. Intraoperative narcotic use will be collected from the medical record.

The standard postoperative medication will include Toradol 30 mg IV unless a patient is 65 years of age or older or has renal or vascular disease. All patients will also receive a prescription for 20 tablets of Oxycodone 5 mg po (or 20 tablets of Hydrocodone 5 mg po or 20 tablets of Hydromorphone 2 mg po, in the event of an allergy/intolerance to Oxycodone). Note will be made of any refills during the eight-week recovery period. Patients will be provided postoperative narcotics in the recovery unit as needed per anesthesia and nursing assessment. If a patient has an allergy to any of the pre or postoperative medications, they will not receive that medication.

The block will contain 10 mL 0.25% bupivacaine hydrochloride. Bupivacaine hydrochloride is a long-acting anesthetic that is FDA-approved for local anesthesia (subcutaneous) and is routinely used at the time of laparoscopic surgery (see attached FDA approval letter and labeling). Adverse effects of bupivacaine are rare and often dose-related. Adverse effects include nausea/vomiting, anxiety, dizziness, blurred vision, and tinnitus. Toxicity can result in bradycardia, hypotension, arrhythmia, hypoventilation, apnea, and cardiac arrest. The presacral block will contain 25 mg of bupivacaine (10 mL of 0.25% bupivacaine, 2.5 mg/mL)

and the incisional block will contain 50 mg of bupivacaine (20 mL of 0.25% bupivacaine, 2.5 mg/mL) for a total dose of 75 mg. The maximum safe dose of bupivacaine is 2 mg/kg therefore all patients with a weight over 37.5 kg (82.5 lbs) will be safe to receive this dose. This weight threshold encompasses nearly all women over age 18. In the very unlikely event that a patient weighs less than this, the incisional block will be reduced accordingly. No additional bupivacaine will be used during the procedure. Patients with an allergy to bupivacaine will be excluded from the study.

Patients will be charged for the bupivacaine anesthetic as it is a standard component of a laparoscopic hysterectomy and is routinely injected in the incisions for local anesthesia. All patients will be receiving the anesthetic in the incisions regardless of the treatment arm. Only patients in the SHPB arm will also receive the anesthetic in the presacral space. This is not anticipated to add cost to the procedure as all patient in the study will receive this medication.

XII. Outcomes:

The primary outcome will be immediate postoperative patient pain scores (within 4 hours) using the Visual Analog Scale (VAS) in the recovery unit. The secondary outcomes will be intraoperative and postoperative opioid consumption as well as VAS pain scores from the Brief Pain Inventory (BPI) as recorded in a patient diary for one week following surgery. Subgroup analyses will be performed on patients undergoing a hysterectomy for pelvic pain and patients who undergo a laparoscopic hysterectomy without concomitant procedures.

XIII. Participant timeline:

Participation starts with enrollment and an eligibility screen. Eligible patients who agree to participate will be consented on the day of surgery. Patients will undergo surgery and be followed up to eight weeks postoperatively.

XIV. Sample size:

A sample size was determined using prior data on the increased percentage of patients with low VAS scores following SHPB and abdominal hysterectomy.¹⁰ Sixty-three percent of women in the ropivacaine group had a VAS pain score less than 4 at two hours postoperatively, compared to 25% in the placebo group ($p=0.015$). A two-sample comparison of proportions with a beta error of 0.2, alpha error of 0.05, and 10% loss to follow-up, therefore requires a sample size of 58 patients. Accounting for heterogeneity in the patient population we aim to recruit 100 patients, with 50 in each treatment arm. Patients will be enrolled at BWH, FH, UNC and GWU, with approximately 50 patients coming from BWH/FH, 30 patients from UNC and 20 patients from GWU. We expect to enroll approximately 20 patients per month between the three sites. Data collection is anticipated to take approximately seven months, accounting for postoperative evaluation up to eight weeks after surgery.

XV. Recruitment:

Recruitment begins at the initial consult visit. The surgeon will explain the study, and then ask the patient if they would like to hear more about it. Only patients that affirm that they are

interested will then be given a description of the study protocol and a copy of the consent form to take home with them (Appendix “SHPB Consent Form”). If a subject decides they do not want to participate, a decline card will be included in the materials. A research assistant will also contact subjects by phone to answer any questions regarding the study. Patients who remain interested in participating will be formally consented on the day of surgery by one of the participating surgeons.

XVI. Assignment of interventions, allocation concealment, and implementation:

Patients will be randomized on the day of surgery after informed consent has been obtained. Subjects will be randomized using urn randomization with a 1:1 allocation of treatment and placebo, stratified by the three sites (BWH/FH, UNC and GWU). Randomized allocation of the treatment arms will be concealed in sequentially-numbered, opaque, sealed envelopes. The randomization sequence and concealed allocation envelopes will be prepared by a research assistant and unknown to the remainder of the study staff.

Patients will be randomized to two treatment groups: one group will receive the SHPB, and the other will receive no block. Patients will be randomized after informed consent is confirmed on the day of surgery. Subjects will be randomized using urn randomization with a 1:1 allocation of treatment and placebo, stratified by the three sites (BWH/FH, UNC and GWU). Randomized allocation of the treatment arms will be concealed in sequentially-numbered, opaque, sealed envelopes. The randomization sequence and concealed allocation envelopes will be prepared by a research assistant and unknown to the remainder of the study staff. A placebo arm (e.g. presacral injection of saline) was not designated given little to no anticipated benefit of a sham block. For the treatment arm, the risks of presacral injection are anticipated to be very rare and superseded by the potential benefit of reduced postoperative pain as demonstrated in patients undergoing abdominal hysterectomy.¹⁰

XVII. Blinding:

Patients will be blinded to the treatment arm; however, the surgeon and operating room staff will know if a patient has been randomized to receive the block during the hysterectomy. Nurses in the recovery unit and on the inpatient floors will also be blinded to the treatment arm. The Medication Administration Record will document a blinded medication for patients in the trial to reduce the risk that staff caring for patients outside the operating room become aware of the treatment arms.

XVIII. Data collection methods:

Postoperative pain scores will be collected by a registered nurse upon admission to the recovery unit, and at every hour for four hours or until the patient is discharged. Most patients are discharged home on the same day as surgery with a recovery unit stay between two to six hours depending on the patient. If a patient is admitted to the hospital, the worksheet will be completed by the recovery unit nurse for as long as the patient is in the recovery unit and completed by the floor nurse for a total of four hours postoperatively. Pain scores will be

collected using the Visual Analog Scale to ask patients their pain level on a scale of 0 to 10, where 0 indicates no pain and 10 indicates the worst pain imaginable.

Intraoperative and immediate postoperative opioid consumption will be collected from the Medication Administration Record. The nursing staff will also be asked to complete a recovery worksheet that details the VAS pain score and opioid administration on admission to the recovery unit and every postoperative hour until four hours or the patient is discharged (Appendix “SHPB RN Worksheet”). The nursing staff will also be asked to note the total time the patient was in the recovery unit. Patients will also be asked to complete a daily diary for one week following the procedure, which details their pain level and daily opioid consumption (Appendix “SHPB Patient Diary”).

Patients will be followed for eight weeks after surgery to assess for the occurrence of any postoperative complications. Detailed patient and procedure characteristics including age, race, body mass index, parity, surgical history, surgery indication, procedure type, and surgical approach will also be collected.

No additional follow-up visits will be required; however, the patient will be asked to return their postoperative diary at their routine postoperative visit (approximately four weeks after surgery). To avoid loss to follow-up, patients will be contacted one to three days after surgery or discharge to remind them to complete the daily diary for one week postoperatively. Patients who have a prolonged hospital stay or who are readmitted to the hospital during the first postoperative week will be reminded to complete the diary as an inpatient, and their narcotic consumption obtained from the medical record. Patients who do not schedule a routine postoperative visit or who forget to bring the diary to their postoperative visit will be contacted by phone or mail and a stamped and addressed envelope sent to their home address for them to return the diary.

XIX. Data management:

All healthcare personnel involved in this study will be responsible for completing correct operative and postoperative data. Patients will be asked to complete a daily postoperative diary which they will return at their postoperative visit. All other data points will be abstracted from patient medical records by research assistants. A minimum number of persons will be involved with the data abstraction in an attempt to decrease introduction of bias. The research assistants will also keep a copy of all source documents such as informed consent on file. All data will be kept in password-protected computer systems, locked file cabinets, and offices accessible only to study staff.

XX. Statistical methods:

Statistical analysis will be performed to test the null hypothesis that there is no difference in VAS pain scores or opioid consumption following laparoscopic hysterectomy with and without a SHPB. The primary analysis will be intention to treat, i.e. those patients randomized to the two treatment arms regardless of the intervention or outcome assessment. The primary outcome (immediate postoperative VAS pain scores in the recovery unit for four hours) will

be treated as continuous as well as dichotomized variables and compared using Student's t-tests if continuous and normally distributed, Wilcoxon tests if continuous and non-normally distributed, and Chi-square tests if dichotomized. A linear regression will be performed to adjust for the two participating sites. As patients are randomized to the two treatment groups, no additional adjustment for potential confounding variables is anticipated to be necessary. Subgroup analyses will be performed on patients undergoing a hysterectomy for pelvic pain and patients who undergo a laparoscopic hysterectomy without concomitant procedures. The final analysis will be conducted at the 0.05 level of significance and the interim analysis will be conducted at the 0.002 level of significance (to minimize type I error). Statistical analysis will be performed using appropriate statistical software and with the assistance of a biostatistician.

XXI. Data monitoring:

The principal investigator will review and investigate any study-related complications, if they occur. An analysis of the data will be performed as necessary pursuant to any complications observed, and at the study mid-point. The principal investigator will be in charge of deciding if the study should be stopped based on these analyses. There will be continuous monitoring of events by the principal investigator and prompt reporting of complications to the IRB, in accordance with the study's Data and Safety Monitoring Plan (DSMP). The principal investigator will also keep track of investigator deviations in terms of informed consent processes and the study protocol, and all repeat deviations will be reviewed.

Any unanticipated adverse events or risks to subjects will be reported to the Partners Human Research Committee (PHRC) in accordance with PHRC unanticipated problems reporting guidelines. Adverse events will be reported according to pre-established guidelines such that the relationship of the risks and benefits to subjects participating remains acceptable throughout the conduct of the study. Reports of unanticipated problems involving risks to subjects or others will be tracked on an adverse event tracking log and submitted through Insight/IRB within five working days/seven calendar days of the date the investigator first becomes aware of the problem. Adverse events and minor deviations tracking logs will also be maintained in-house.

XXII. Harms:

Great care will be taken to use the correct dose of each medication and avoid intravascular placement. Resuscitative equipment will be immediately available should an adverse event occur. Should an unforeseen adverse event arise that appears related in any way to the study, the principal investigator will halt the study and report the event to the IRB.

With regard to the risk of disclosure of confidential patient information, all possible precautions will be taken to ensure the confidentiality of study data. Any identifying information will be kept in password-protected computer systems or in locked file cabinets accessible only to the study staff.

XXIII. Auditing:

The data will be audited by the IRB at their discretion.

ETHICS AND DISSEMINATION

XXIV. Research ethics approval:

IRB approval will be obtained at participating sites.

XXV. Protocol amendments:

Protocol amendments will be communicated to the IRB and approval obtained prior to implementation.

XXVI. Consent or assent:

Informed consent will be obtained by participating surgeons on the day of surgery. Eligible subjects will be contacted prior to surgery and provided details of the trial, a copy of the consent form, and a decline card.

XXVII. Confidentiality:

Confidential patient information and any identifying information will be kept in password-protected computer systems or in locked file cabinets accessible only to the study staff.

XXVIII. Declaration of interests:

The investigators declare no conflicts of interest.

XXIX. Access to data:

Data access will be restricted to study investigators and research assistants.

XXX. Ancillary and post-trial care: None

XXXI. Dissemination policy:

Subjects will be informed of the treatment arm they were assigned to at their follow-up visit. Trial results will be publicly available upon publication of the study. Authorship eligibility will include those investigators involved in major portions of the study design, collection, management, analysis, interpretation of results, or writing of the report.

APPENDICES

XXXII. Informed consent materials: Appendix

XXXIII. Biological specimens: None

XXXIV. Images:

Figure 1. Laparoscopic view of the presacral space demonstrating tenting of the peritoneum prior to injection of the superior hypogastric block.

REFERENCES

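### Preoperative opioid use is neither listed for collection nor used in the analysis, which can cost precision on the one-week diary opioid total, a secondary outcome

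*Combined protocol and SAP*

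**What the plan says.** Section VII hypothesizes that the block reduces both pain scores and opioid consumption. Section XII makes opioid use secondary: "The secondary outcomes will be intraoperative and postoperative opioid consumption". It does not define the quantity as net of what the patient took before surgery.

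Section X includes chronic pain by design: "specifically, patients with chronic pain syndromes will not be excluded so as to evaluate the efficacy of SHPB in this population". The exclusions begin "The exclusion criteria include patients who are unwilling to consent, who have an allergy to block medications used in the trial" and go on to sacropexy, laparotomy and unsafe anatomy. None concerns existing opioid use.

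Section XVIII gives two main sources for the opioid data. For the early period, "Intraoperative and immediate postoperative opioid consumption will be collected from the Medication Administration Record", with a nurse worksheet alongside. For the first week there is a patient diary, "which details their pain level and daily opioid consumption", supplemented by the medical record for patients who are in hospital during that week. Nothing in the text separates usual from new opioid. The characteristics named for collection are "age, race, body mass index, parity, surgical history, surgery indication, procedure type, and surgical approach will also be collected". Preoperative opioid use and chronic pain status are not among these eight.

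Section XVI stratifies by site only. Section XX adjusts for site and then says that "no additional adjustment for potential confounding variables is anticipated to be necessary". Neither planned subgroup (pelvic pain as indication, no concomitant procedure) is defined by opioid use.

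**The concern.** A single block at surgery is not expected to change a dose that a patient takes every day for a long-standing condition. If such doses enter the diary, the one-week total is the sum of a part the block might reduce and a part it cannot. The second part is zero for most patients and may be large for a few, so it can dominate the spread of the outcome.

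The stake is precision and interpretation. With 50 per arm, a handful of habitual users can hide a real saving in new opioid use, or can land unevenly and shift the observed difference by chance. Without a baseline record, nobody could tell afterwards which had happened. If the adjustment is chosen after the results are seen, it is post hoc.

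The point concerns mainly the diary total. Intraoperative and recovery-unit opioid should contain little or no maintenance dose.

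**Working it through.** **The plan's own figure.** Section XIV bases its sample size on 63% versus 25% with VAS below 4, alpha 0.05 and power 0.80. A two-sided comparison of proportions without continuity correction gives 26 per arm, 52 in total, and 52/0.90 = 57.8, rounded up to 58. The stated 58 reproduces. It concerns the VAS outcome and does not depend on this point. No power is stated for opioid consumption.

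**Inputs for the opioid illustration.** From the protocol: 50 per arm, a seven-day diary, significance level 0.05. Assumed, because the protocol gives none of them: new one-week use is gamma-distributed with mean 60 and SD 45 morphine-mg equivalents in controls; the block lowers new use by 40% (24 mg); and a share q of patients also takes a fixed home dose of d mg/day, all of it entered in the diary.

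**Added variance.** A share q taking 7d mg over the week adds q(1−q)(7d)² to the control variance of 45² = 2025.

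| q | d (mg/day) | added variance | ratio to new-use variance |
|---|---|---|---|
| 0 | any | 0 | 1.00 |
| 3% | 15 | 0.0291 × 105² = 321 | 1.16 |
| 5% | 30 | 0.0475 × 210² = 2095 | 2.03 |
| 10% | 30 | 0.09 × 210² = 3969 | 2.96 |
| 15% | 60 | 0.1275 × 420² = 22491 | 12.1 |

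**Power for a comparison of means, by hand.** Scaling new use by 0.6 gives a treated-arm SD of 27 and variance 729. The standard error is √[(2025 + 729 + 2 × added variance)/50], and power is Φ(24/SE − 1.96).

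- No habitual users: SE = √(2754/50) = 7.42; 24/7.42 = 3.23; power about 90%.
- 5% on 30 mg/day: SE = √(6944/50) = 11.78; ratio 2.04; power about 53%.
- 10% on 30 mg/day: SE = √(10692/50) = 14.62; ratio 1.64; power about 37%.

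**Power by simulation of the same model.**

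| habitual users | comparison of means | Wilcoxon |
|---|---|---|
| none | about 92% | about 86% |
| 5% on 30 mg/day | about 55% | about 78% |
| 10% on 30 mg/day | about 38% | about 70% |

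The hand values agree with the simulated means column to within about 2 points. In the 5% case, adding preoperative daily dose as a covariate restores power to about 90%. That is the ideal case, in which the home dose is recorded without error and taken unchanged all week.

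**Chance imbalance.** Suppose 5 of 100 patients take 30 mg/day. With 50 per arm, a split of 4–1 or 5–0 in either direction has probability 36% (hypergeometric). A 4–1 split moves the difference in mean weekly use by 3 × 210/50 = 12.6 mg, about half of the assumed 24 mg effect. The only opioid effect in the protocol is the difference in medians from the earlier abdominal hysterectomy trial, 72.4 − 55.8 = 16.6 mg. It is useful for scale only, since the protocol does not say that it covers a one-week window.

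**The case against.** The strongest reply is that little here is certain. The list in section XVIII is introduced by *including*, and the diary and both worksheets are appendices that are not shown. A reader might infer that the trial does not record preoperative opioid use, or that the diary counts usual opioid as postoperative consumption. The text supports neither. It supports only that preoperative use is not listed and that no counting rule is stated. This part of the reply stands. Even if the field sits on a worksheet, however, section XX does not use it.

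The second reply concerns size. Chronic pain is not the same as daily opioid use. User share, dose and SD are all assumed, and variance ratios from 1.16 to 12.1 do not establish that the effect is material. This also stands: the loss is zero if no one enrolled is a habitual user.

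The third reply concerns the test. It is tempting to say that a doubled variance makes 50 per arm worth 25, but that holds only for a comparison of means. Section XX names Wilcoxon for non-normal data, and under the same assumptions Wilcoxon loses about 8 points rather than 37. That limits the damage, but the sentence naming the tests is written for the primary outcome, no test is named for opioid use, and the site adjustment is a linear regression.

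Finally, randomization removes systematic bias, and section XX relies on it to justify not adjusting. That answers confounding but not lost precision, which is the whole of this point.

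**Conclusion.** The point holds as a cheap improvement to one secondary outcome, the one-week diary opioid total. The protocol deliberately admits patients among whom habitual opioid use is plausible, does not list that use for collection, does not say how it is counted, and plans no analysis that accounts for it.

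The size cannot be fixed from the protocol. On the assumptions above, 5% of patients on 30 mg/day costs about 37 points of power for a comparison of means (92% to 55%) and about 8 points for Wilcoxon (86% to 78%). At 10% the power is about 38% and 70%. With no habitual users nothing is lost.

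A reader might go further and infer that the treatment comparison is biased, that the whole opioid objective turns on a few patients, or that the primary result is at risk. The protocol supports none of these. Allocation is randomized, the intraoperative and recovery-unit amounts are largely free of maintenance doses, and neither the VAS outcome nor the 58/100 sample size depends on how opioid is counted.

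**What to change.** **Section XVIII.** Add preoperative opioid use (yes/no and usual daily dose) to the collected characteristics, abstracted from the medical record that research assistants already review. Take the value that stood before randomization.

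**Section XX.**
- State how a patient's usual opioid is counted in the diary total.
- Analyze one-week opioid consumption adjusted for site and preoperative daily opioid dose, with zero for non-users.
- Report a sensitivity analysis in patients with no preoperative opioid, using Wilcoxon if the data are skewed. Because the restriction is on a baseline characteristic, the comparison is still between randomized groups.

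**Cost.** A few minutes of abstraction per patient and a short addition to section XX. If few patients have a nonzero dose (about 5 of 100 in the 5% illustration), the dose term may rest on a handful of high-leverage values, which is why the non-user analysis is reported alongside. Eligibility, prescribing, the primary outcome and the sample size do not change.

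### Hour 3 and 4 pain scores are lost when a patient goes home but kept when a patient is admitted, and the planned tests have no way to handle the gap

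*Combined protocol and SAP*

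**What the plan says.** Section XII gives the primary outcome as "immediate postoperative patient pain scores (within 4 hours) using the Visual Analog Scale (VAS) in the recovery unit". Section XX restates it as "immediate postoperative VAS pain scores in the recovery unit for four hours" and plans a t-test, a Wilcoxon test or a chi-square test, with a linear regression to adjust for site. Neither section names a time point or a per-patient summary, and neither has a rule for scores that were not taken. The primary analysis is by intention to treat.

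Section XVIII contains two stopping rules for these scores:

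- Patients who go home are scored on arrival in the recovery unit and then "at every hour for four hours or until the patient is discharged". The nurse worksheet repeats this: "every postoperative hour until four hours or the patient is discharged".
- For admitted patients the worksheet continues after transfer and is "completed by the floor nurse for a total of four hours postoperatively".

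The same section says that most patients go home on the day of surgery, with a "recovery unit stay between two to six hours depending on the patient". Nurses also "note the total time the patient was in the recovery unit", but the analysis does not use this time.

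**The concern.** Whether a patient has a 3 h or 4 h score is decided after randomization, by when she is discharged or whether she is admitted. Section VII hypothesizes that the block lowers pain and opioid use, and either could change readiness to leave. If so, the patients still being scored at 3 h and 4 h are no longer the randomized groups. Intention to treat keeps each patient in her arm but does not supply a score that was never taken, and two-sample tests simply drop it.

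The definition and the collection rule also disagree. Read literally, sections XII and XX exclude a score taken on the floor, yet section XVIII collects it. Two analysts could build different primary datasets from the same worksheets.

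**Working it through.** **1. The plan's own figure.** Section XIV uses 63% versus 25% with VAS below 4 at 2 h, alpha 0.05 (taken as two-sided), power 80% and 10% loss. With p̄ = (0.63 + 0.25)/2 = 0.44:

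n per arm = [1.96·√(2·0.44·0.56) + 0.842·√(0.63·0.37 + 0.25·0.75)]² / 0.38² = (1.376 + 0.546)² / 0.1444 = 25.6, so 26.

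Total 52; 52/0.9 = 57.8, so 58. The stated 58 is reproduced and is not in dispute. It rests on the 2 h score, and 2 h is the shortest stay in the stated range.

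**2. Which scores exist under section XVIII.**

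| Patient | 0 to 2 h | 3 h | 4 h |
|---|---|---|---|
| Home between 2 h and 3 h | yes | no | no |
| Home between 3 h and 4 h | yes | yes | no |
| Home after 4 h | yes | yes | yes |
| Admitted | yes | yes | yes (may be on the floor) |

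The first two rows fall within the stated two to six hours, so missing late scores are expected by design.

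**3. Possible size.** The documents give no admission rate, discharge criteria or VAS standard deviation, so every input below is assumed. Differences are control minus block at 4 h.

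*Set A.* Control means fall from 5.0 to 3.7 over 4 h; between-patient SD 1.5, within-patient SD 1.0; no discharge before the 2 h score.

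| Discharge per hour | Admission | Scored at 4 h, control / block | True | Observed |
|---|---|---|---|---|
| 60%, unrelated to pain | 15%, unrelated to pain | 29% / 29% | 0.96 | 0.96 |
| 60% if VAS < 4 | 15%, unrelated to pain | 63% / 48% | 0.96 | 0.93 |
| 90% if VAS < 4 | about 15%, rising with pain | 51% / 18% | 1.85 | 1.42 |
| 90% if VAS < 4 | 30%, unrelated to pain | 60% / 37% | 1.85 | 2.06 |

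The third row is (1.85 − 1.42)/1.85 = 23% too small. The fourth is (2.06 − 1.85)/1.85 = 11% too large. In the fourth row the observed mean is too high by 0.57 in control and by 0.37 in block, so the arm that loses more scores has the smaller shift.

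*Set B.* Control means fall from 5 to 3.5; SD 2.2; within-patient correlation about 0.65; scores bounded at 0 and 10; discharge after the 2 h or 3 h score with probability 90% if VAS < 4 and 10% otherwise. The true 4 h difference is about 0.84.

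| Admission | Observed | Change |
|---|---|---|
| none | 0.49 | (0.84 − 0.49)/0.84 = 42% smaller |
| about 15%, rising with pain | 0.63 | 25% smaller |
| 15%, unrelated to pain | 0.81 | 4% smaller |
| 30%, unrelated to pain | 0.86 | 2% larger |

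With similar inputs but weaker dependence (50% versus 10%, no admissions), the observed difference is 0.90 against 0.92. The cost is then mainly lost data: 51% of control and 60% of block 4 h scores are missing.

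**4. Other analyses of the same data.** A per-patient mean of available scores moves by at most about 0.1 point in set A and about 0.04 in set B. A likelihood-type estimate of the 4 h difference, which uses each patient's earlier scores, gives 0.82 to 0.85 in every set B row against the true 0.84.

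**The case against.** A reader might infer that later scores come from patients in more pain, more so in whichever arm recovers faster, and that the block's effect will therefore be understated. The documents do not support that. They do not link discharge or admission to pain; section XVIII says only that the stay depends on the patient. Even if pain drives discharge, the direction is not fixed, as the fourth row of set A shows. What does follow from pain-driven discharge is that the arm with less pain loses more scores. The 42% figure also assumes no admissions, whereas section XVIII expressly provides for them.

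The stronger objection is that no section plans a stand-alone 4 h comparison. A per-patient mean is barely affected, and naming the 2 h score as primary would remove most of the problem. This limits the size of the concern but does not dispose of it: sections XII and XX commit to neither the 2 h score nor any summary, so an exposed 4 h or last-score analysis remains open. The selection also arises from a stated collection rule, which remains until the analysis deals with it.

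It can also be objected that asking patients to record hourly scores after going home would mix self-recorded with nurse-recorded scores, possibly unequally by arm. That is fair, and the fix does not depend on it.

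**Conclusion.** The concern holds in a limited form. The text establishes three things: unequal stopping rules, an outcome location that contradicts the collection rule, and tests that use only what was observed. Missing 3 h and 4 h scores are to be expected under the stated stays.

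Bias is conditional on discharge or admission depending on pain. If it does, a 4 h comparison can be wrong in either direction, by about 42% too small to about 11% too large under the assumed inputs. If the dependence is weak, bias is near zero and the cost is lost precision. Scores through 2 h, and a per-patient mean, are little affected. The exact percentages should not be read as forecasts, because the documents supply none of the inputs that determine them.

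**What to change.** - **Section XX:** analyse all scores from recovery admission to 4 h with a repeated-measures model containing arm, time, arm-by-time and site, so that scores before discharge inform the later ones. State which contrast from the model is primary.
- **Section XX:** add a sensitivity analysis limited to scores through 2 h, the time point behind the sample size.
- **Sections XII, XVIII and XX:** make the definition consistent by stating that floor scores up to 4 h count toward the primary outcome.
- **Reporting:** give the number of patients scored at each hour by arm.

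The cost is a few wording changes and slightly more analysis work; no extra data are needed. The model relies on scores being missing at random given those already recorded. That is reasonable if discharge follows recorded pain, but less secure if it follows something unrecorded, which is why the 2 h analysis should accompany it. Self-recorded hourly scores after discharge are optional.
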